8.3 Analysis of Efficacy and Safety

The efficacy measures are conducted on the per-protocol (PP) and intent-to-treat (ITT) basis. The per protocol will be defined as (1) The drug compliance is at least 80% (2) Subjects have completed data to determine the primary endpoint. (3) Subjects cannot have major protocol deviation. The major protocol deviation will be defined as (1) Inclusion or exclusion criteria not satisfied. (2) Not permitted concomitant medications (3) Wrong randomized treatment prescribed. An intent-to-treat (ITT) basis will be defined as the data are analyzed by the treatment groups to which the randomized patients who take at least one dose of study medication and have any post-baseline safety data collected. The safety measures are conducted on the patients who take at least one dose of study medication. The data are analyzed utilizing the last observation carried forward (LOCF) technique to impute the missing data.

The efficacy and safety information recorded on CRF will be summarized by tables presented in frequency and percentage for categorical variables, in mean with SD as well as median with the minimum and maximum for continuous variables. The comparison between three groups will be analyzed by nonparametric method as appropriate. All adverse events will be summarized with coding term, severity, relationship to study drug by frequency tables with the counts and percentage. In addition, serious adverse events will be listed with event narration.

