3.1 General Design

Table 11. Summary of general design

	Phase II Part II
Design	Double-blind, randomized, parallel group, placebo-controlled
ADHD patients	Stage I: 69 Stage II: 30
Treatment	Randomly assigned on a 1:1:1 basis to one of the three arms: (1) 1 PDC-1421 Capsule plus 1 placebo TID (2) 2 PDC-1421 Capsule TID (3) 2 Placebo TID for 56 days There will be an interim analysis between stage I and stage II.
Assessment interval	Biweekly
Efficacy and safety evaluation	
 • Primary endpoint: efficacy measurement (ADHD-RS-IV) • Secondary endpoints: other efficacy and safety measurements (ADHD-RS-IV, CAARS-S:S, CGI-I, E-SCT, ECG, vital sign, physical examination, hematology, blood chemistry and concomitant medication evaluation)

The Screening phase is intended for diagnosing and assessing the patient for possible inclusion in the study and for providing an adequate washout period. The targeted population of this Part II study is 99 subjects who met the intent-to-treat basis.

[figure not shown]
Part II is a randomized, double-blind, placebo-controlled, parallel-group study.

Stage I: Sixty nine subjects will be randomly assigned on a 1:1:1 basis to one of the three treatment arms (1 PDC-1421 Capsule plus 1 placebo TID, 2 PDC-1421 Capsule TID, 2 placebo TID). Each subject will be treatment for 8 weeks and will return for visit biweekly during the treatment period.

An interim analysis: An interim analysis will be conducted to evaluate the efficacy of PDC-1421 and to decide whether it is necessary enter the second stage of Part II. (See [Section 8](#) for evaluation details.)

Stage II: Thirty subjects will be randomly assigned on a 1:1:1 basis to one of the three treatment arms (1 PDC-1421 Capsule plus 1 placebo TID, 2 PDC-1421 Capsule TID, 2 placebo TID). Each subject will be treatment for 8 weeks and will return for visit biweekly during the treatment period.

Figure 2. General design of procedure

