8.1 Sample Size Determination

In part II, this is a small proof-of-concept study to evaluate low-dosed PDC-1421 arm, high-dosed PDC-1421 arm and placebo arm in the treatment of ADHD. A two stage design developed by Jung (2008) with $\alpha=0.15$ and power=80% will be used. We estimated that the PDC-1421 is considered non-effective if the response rate based on ADHD Rating Scale – Investigator Rated (ADHD-RS-IV) is 20 % or lower and is worth further study if the response rate is 40 % or higher. At the first stage, we recruit 23 subjects for each group. If the difference between the numbers of responders for any PDC-1421 arm and control arm is greater or equal to 0, we proceed to the second stage. We will recruit 10 subjects for each group at the second stage. If the difference between the accumulated numbers of responders for any PDC-1421 arm and control arm is less than 4, we reject the drug. The minimum sample size required is to recruit 69 subjects, while the maximum sample size is 99. No multiple comparison will be applied.

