5.3 Statistical Methods Planned in the Protocol and Determination of Sample Size

5.3.1 Populations for Analysis

The INTENT-TO-TREAT (ITT) POPULATION consists of all randomized subjects who receive at least one dose of study medication and fulfill all inclusion, exclusion criteria and have any post-baseline safety data collected.

The PER-PROTOCOL (PP) POPULATION is defined as (1) The drug compliance is at least 80% (2) Subjects have completed data to determine the primary endpoint. (3) Subjects cannot have protocol deviation. The protocol deviation will be defined as (1) Inclusion or exclusion criteria not satisfied. (2) Not permitted concomitant medications (3) Wrong randomized treatment prescribed.

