6.2 Data Sets Analyzed

Two study populations are intention-to-treat (ITT) population and per-protocol (PP) populations which are defined in section 5.3.1.

The efficacy evaluations will be performed on both of the ITT and PP datasets while the safety evaluations will be performed on the ITT dataset. The primary conclusion will be made for the primary endpoint on the ITT population. Demographic and baseline (Visit 2) characteristics will be performed on the ITT population.

Sample size, mean, 95% confidence interval of mean, median, standard deviation, inter-quartile range, maximum and minimum will be summarized for continuous variables. For categorical variables, the frequency and percentage will be provided.

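### The efficacy ITT set requires post-baseline safety data, so the denominators of the primary response proportions depend on how very early leavers were followed, which can differ by arm

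*Protocol*

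**What the plan says.** Protocol 8.3 analyses efficacy on an ITT basis made up of "randomized patients who take at least one dose of study medication and have any post-baseline safety data collected". SAP 5.3.1 also asks for one dose and adds that subjects must "fulfill all inclusion, exclusion criteria and have any post-baseline safety data collected". (The SAP's eligibility condition is a separate matter.) Neither document requires a post-baseline efficacy score. SAP 6.2 gives the set its weight: "The primary conclusion will be made for the primary endpoint on the ITT population".

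The safety set differs between the documents. Protocol 8.3: "The safety measures are conducted on the patients who take at least one dose of study medication". SAP 6.2 has only the ITT and PP populations and assigns safety to the first: "while the safety evaluations will be performed on the ITT dataset".

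Missing data are handled by LOCF (Protocol 8.3 and 8.4; SAP 6.6.1 and 6.8.1). Neither document says what happens to a subject who has only a baseline score.

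**The concern.** The condition applies after randomisation and has nothing to do with ADHD-RS-IV. It matters for subjects who take a dose and leave before Visit 3.

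In Protocol Table 15 no assessment falls between Visit 2, where baseline data are taken before dosing, and Visit 3 at week 2. No early-termination visit is listed. Post-baseline safety data from that window can come only from unscheduled contact. Protocol 4.5 makes such contact uneven: subjects withdrawn for adverse events must be followed to an outcome, while others need give no reason and have no stated follow-up. Protocol 1.4.1 reports more gastrointestinal discomfort than on placebo in earlier studies, so a difference between arms in what gets recorded is plausible.

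Two subjects with the same efficacy information, namely none, can thus be treated differently: one stays in the denominator and the other is removed. If the share removed differs by arm, the ITT proportions no longer compare the groups as randomised.

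**Working it through.** **1. The plan's own design, and what does not move.** Inputs from Protocol 8.1: 23 then 10 per arm, response rates of 20% and 40%, continue if the difference in responder counts is at least 0, reject the drug if the cumulative difference is below 4. With D1 and D2 the count differences in the two stages, the exact probability P(D1 ≥ 0 and D1 + D2 ≥ 4) for one active arm against placebo is 0.139 at 20% v 20% and 0.801 at 40% v 20%. This agrees with the stated α of 0.15 and power of 80%. A leaver with no post-baseline score adds 0 responders whether kept or deleted, so D1 and D2 are unchanged. The same holds for the count comparison in SAP 6.6.1.

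**2. What does move.** For an arm of N with r responders and e early leavers, the reported proportion is r/N if the leavers are kept as non-responders and r/(N − e) if they are deleted.

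Assumptions: 33 per arm, 13 active and 7 placebo responders (near the design rates), 3 leavers per arm. The documents give no leaver numbers, and these counts are not trial results. The p-values are Pearson chi-square, without continuity correction, for one active arm against placebo.

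| Leavers deleted | Active | Placebo | Difference (points) | p |
|---|---|---|---|---|
| None | 13/33 = 39.4% | 7/33 = 21.2% | 18.2 | 0.108 |
| Placebo only | 13/33 = 39.4% | 7/30 = 23.3% | 16.1 | 0.171 |
| Active only | 13/30 = 43.3% | 7/33 = 21.2% | 22.1 | 0.060 |
| Both arms | 13/30 = 43.3% | 7/30 = 23.3% | 20.0 | 0.100 |

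At 23 per arm with 9 v 5 responders and 3 leavers per arm, all kept gives 9/23 − 5/23 = 17.4 points. Deleting only the placebo leavers gives 9/23 − 5/20 = 14.1. Deleting only the active leavers gives 9/20 − 5/23 = 23.3.

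**3. Expected bias under less extreme splits.** Let p be the true response rate among all dosed subjects, d the fraction leaving early, and q the fraction of leavers with qualifying safety data. The reported rate is p / [1 − d(1 − q)].

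- p = 20% in both arms, d = 10%, q = 80% active and 20% placebo: 0.20/0.98 = 20.4% and 0.20/0.92 = 21.7%, a bias of −1.3 points.
- Smallest on the grid, d = 5%, q = 60% and 30%: 0.20/0.980 = 20.4% and 0.20/0.965 = 20.7%, −0.3 points.
- Largest, d = 15%, q = 100% and 0%: 0.20/1.00 = 20.0% and 0.20/0.85 = 23.5%, −3.5 points.
- At 40% v 20%, d = 10%, q = 80% and 20%: 0.40/0.98 − 0.20/0.92 = 19.1 points against a true 20.

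**4. Is a retained leaver a non-responder?** Carrying the baseline score forward gives 0% improvement and hence a non-responder, but that is an inference. The code in SAP 6.6.1 processes by subject and visit and clears the retained value at FIRST.visit. With one total score per visit, that is every record, so nothing is carried and the value stays missing. Text and code thus give different outcomes for the same subject.

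**The case against.** The strongest reply is that little of the final analysis is exposed. SAP 5.4 drops the between-arm chi-square test after termination. For categorical variables SAP 6.2 plans only frequency and percentage. The stage rules use counts. All of this stands. What remains is the descriptive ITT proportions by arm, which SAP 6.6.1 still reports, and the test as planned in Protocol 8.2.

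Second, a reader might infer that entry to the set turns on whether an adverse event was recorded. The documents do not say that. Any post-baseline safety data qualify. Protocol 7.1 counts vital signs, laboratory tests, ECG, physical examination and C-SSRS, and Protocol 5.2 allows several of these remotely in a public health emergency. Whether a recorded absence of adverse events qualifies is undefined. The link to adverse events is one of likelihood, through Protocol 4.5.

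Third, if the SAP code is taken literally, kept and deleted leavers both lack a response value and the contrast between them largely disappears. That is fair, but it shows that the rule is unsettled, not that it is sound.

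Fourth, a reader might see a contradiction between "The targeted population of this Part II study is 99 subjects who met the intent-to-treat basis" in Protocol 3.1 and "The minimum sample size required is to recruit 69 subjects, while the maximum sample size is 99" in Protocol 8.1. There is none: a target and a cap of 99 are both met whenever no randomised subject is excluded.

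Finally, requiring one dose is defensible in a double-blind trial, and nothing here shows harm from it.

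**Conclusion.** The point holds in limited form. The set that carries the primary conclusion is filtered on post-randomisation safety data, and the follow-up rules make that filter uneven for very early leavers. The extreme splits shift the illustrative difference from 18.2 to 16.1 or 22.1 points, with p from 0.108 to 0.171 or 0.060. Those p-values lie on both sides of the design α of 0.15, but the documents set no level for the chi-square test, so this does not amount to a changed conclusion. At equal true rates of 20% the expected bias is about 0.3 to 3.5 points, the upper end needing 15% leavers and complete separation of the arms.

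At equal rates the bias runs against the drug if active arms yield more safety records, and for it if placebo does. At 40% v 20% with a mild split (60% and 30%) the two deletions nearly cancel, leaving 20.1 to 20.2 points against a true 20. Leaver fractions and recording splits are all assumptions. A reader should not infer that the decision to stop or continue was affected, since the count rules do not move.

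**What to change.** In Protocol 8.3 and SAP 5.3.1, delete the post-baseline safety data condition from the efficacy ITT set and analyse randomised subjects in their assigned arm. Keeping the one-dose requirement is acceptable. State that any subject without a post-baseline ADHD-RS-IV counts as a non-responder, likewise as a non-remitter and as not reaching CGI-I of 2 or lower. Bring the code in SAP 6.6.1 into line with that rule.

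In SAP 6.2, run safety on all subjects who took at least one dose, as Protocol 8.3 already states. Without this edit, dropping the one-dose requirement from ITT would bring undosed subjects into the safety tables.

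The cost is small edits to three sections plus the code, no new data, and slightly lower reported response rates in arms with very early leavers. Because the SAP was written after the interim result was known, record the change and its date in SAP 5.4.

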8.4 Premature Termination and Handling of Missing Data

Any premature termination of the study therapy will be recorded in CRF. Listing of the subjects with premature termination will be provided with the dates and reasons. Missing data caused by premature termination will be utilized the last observation carried forward (LOCF).

9. Quality Control and Quality Assurance

9.1 Study Monitoring

The clinical monitor from sponsor-designated contract research organization (CRO) will be responsible for overseeing the progress of a clinical trial to be conducted, recorded, and reported in accordance with the protocol, Standard Operating Procedures (SOPs), GCP, and the applicable regulatory requirements. All written informed consent and CRFs will be carefully reviewed and the accuracy of the data will be validated by clinical monitor. The monitoring can be performed remotely, but it should be documented.

9.2 Sponsor Auditing

Prior to locking the database of safety, the representative of Sponsor's quality assurance department may visit the Investigator's site to implement an audit of study. The audit will to determine the compliance of Investigator with protocol, GCP and applicable regulations. Besides, auditors will assess the accuracy of clinical data record. The Investigator and trial personnel need to cooperate with auditor to facilitate the process of audit.

9.3 Inspected by Regulatory Authorities

Local regulatory authority may visit the Investigator to conduct an inspection of this study and the site. The Investigator must make the trial-related records accessible to regulatory agency inspectors. In addition, the Investigator needs to notify the Sponsor immediately when contacted with regulatory authority for the inspection.

10. Ethical Considerations

10.1 Confidential

All information about study subjects will be kept confidential in accordance with the applicable regulatory requirement, to protect and respect the privacy of study subjects. Only the members performed study-related processes, including trial-related monitoring, audits, IRB/IEC review, and regulatory inspection, could directly access to source data/documents.

10.2 Protocol Amendment

Any amendment to the Protocol which deemed necessary as the study progresses will be fully discussed by Investigators and the Sponsor. A written amendment must be submitted to US FDA and TFDA and the respective Chairman of the IRB, except when the change(s) involves only logistical or administrative aspects of the trial (e.g. change in clinical monitors or change of telephone numbers). Investigator must wait for their approvals of the protocol amendment before implementing the changes. A protocol change intended to eliminate an apparent immediate hazard to trial subjects may be implemented immediately while simultaneously informing FDA /IRB and TFDA/IRB.

When, in the judgment of Chairmen of the IRB, Investigator and/or the Sponsor, the amendment to the Protocol substantially alters the study design and/or increases the potential risk to the subjects, the currently approved written informed consent form will be modified according to the modification. A second informed consent will be obtained from subjects enrolled in the study before further participation.

10.3 Informed Consent

Written informed consent must be reviewed and approved by IRB. Informed consent will be designed to provide detailed information, including explanation of the purpose of this study, the risks and discomforts involved, potential benefits and all basic elements

required by regulatory agencies, to participants. Investigator (or his or her qualified designees) will be responsible for explaining the contents of the informed consent to participants as clear as possible. Once it is felt that the subject understands the implications of participating, the written informed consent form shall be signed by the subject and a witness. The written informed consent will be obtained from each subject before any study related procedures (including any pre-treatment procedures) are performed.

10.4 Institutional Review Board (IRB)

This study is conducted to be consistent with the principles of the Declaration of Helsinki and GCP. This protocol and any supplementary documents, including written informed consent form, subject recruitment advertisements and Investigator's Brochure, must be reviewed and approved by IRB qualified with local legal prescriptions prior to study initiation. The members of IRB are average thirty people, including medical doctors, professors of pharmacology and members whose primary area of interest is in the nonscientific area such as law and social welfare policy. One group of members of IRB meet once a month. Any changes in protocol must be received the IRB approval/favorable opinion in advance of use except for the immediate hazards to trial subjects. Investigator shall submit a status report to IRB at the end of the study. IRB must be notified by the Investigators promptly for all unanticipated problems involving risk to human subjects or others. Investigator is required to maintain an accurate and complete record of all written submissions made to IRB and must agree to share all such documents and reports with the Sponsor and any regulatory agency.

11. Data Handling and Record Keeping

An EDC (electronic data capture) system may be used in this study to handle data in an electronic CRF. Follow the EDC system guideline when using it.

11.1 Data Handling and Collection

11.1.1 Study Specific Binders

Two types of binder will be utilized in this study:

- Subject Binder: Containing informed consent and certain source documents collected for each subject entered the treatment period of the study. Each Subject Binder will have tab dividers for the laboratory printouts. Subject Binders will be kept at each study center.
- Investigator Study File: Documents pertinent to the conduct of this study will be filed in this binder.

11.1.2 Responsibilities of Investigators

The Investigator shall process, prepare and maintain complete and accurate study procedure and documentation in compliance with GCP standards and local laws, rules and regulations. It is the Investigators' responsibility to ensure that the designated CRC for this study at the hospital fully understands his/her responsibilities and has the ability to fulfill all the relevant tasks on behalf of the Investigator in many occasions. For each subject enrolled, a CRF must be completed and signed by the Investigator, no matter if this subject has completed the study or not. The Investigator agree to fully cooperate and assist the clinical monitor in performing their duties, including enabling direct access to the relevant hospital and clinic records. Study documentation will be promptly and fully disclosed to the Sponsor by the Investigator and also shall be made available at the Investigators' site for inspection, copying, review and audit for a reasonable number of times by representatives of the Sponsor or any regulatory agencies. The Investigator agrees to promptly take any reasonable steps that are requested by the Sponsor as a result of an audit

to correct the known error in the study documentation and case report forms. The Investigator shall submit to the Sponsor all original case report forms and all reports required by the Protocol when the clinical study have been completed or terminated.

11.1.3 Responsibilities of Clinical Monitor

Clinical monitor shall frequently inspect the source documents (clinic and hospital subject records) and compare them with the CRF at regular time interval throughout the study, to verify the adherence of study execution to the Protocol and confirm the completeness, consistency and accuracy of the data entered. The monitor will perform source data verification by visually comparison between the entries of the CRF and subjects' records, including informed consent, inclusion/exclusion criteria, key variables, drug administration, adverse experience records and safety variables. Additional monitoring will be required if the error rate is unacceptably high.

11.2 Records Retention

11.2.1 Source Document Retention

Source documents refer to any record pertained to a given subject in the study from which study data is, or could be, obtained or verified. This includes, but not limited to, records, charts, notes and laboratory reports. These records, maintained by the Investigator, shall comply with applicable regulations. At the aspect of ICF keeping, one of the original signed informed consent forms for each participant shall be filed with records kept by the Investigator and the other copy should be given to the subject. Besides, progress notes on each visit to the clinic will be required. The progress note of each visit shall at least contain the date of the visit, a general reference to the procedures completed, general subject status remarks including any significant medical findings, and the signature of the clinician making the entry. In addition, any contact with the subject via telephone or other means that provides significant clinical information, such as adverse events, will also be documented in the progress notes. These will be filed with subject records kept by the Investigator and made available for inspection by authorized personnel.

